16.4 STATISTICAL METHODS

Primary End Point: Average pain intensity over the past 7 days (0–10 numerical rating scale where 0 indicated “no pain” and 10 “worst possible pain”) six weeks and six months after surgery (Dworkin et al., 2005).

Secondary end points: Chronicity of postsurgical pain: Six months after surgery, CPSP will be defined in a dichotomous way (yes/no) as the presence of symptoms 6 months after surgery are reported.

Descriptive statistics (means, SD, medians, n, %) will be calculated in order to present baseline characteristics of the different comparison groups and follow-up measures. To better appreciate the evolution of pain intensity (primary endpoint) during the longitudinal follow-up (baseline to six months after surgery), linear mixed models for repeated measures will be achieved for each of the three comparison schemes described above with the inclusion of the following variables as independent variables to obtain adjusted effects: age, functional outcome score and psychological profile (STAI and PCS scores). This type of analysis is justified by its flexibility in regard to missing data caused by patients lost to follow-up [75] and the possibility to adjust for potential confounders (e.g. patients’ demographics, physical and emotional functioning, clinical characteristics such as medication use or scoliosis parameters). Continuous secondary outcomes will be compared between study groups using similar models. Categorical secondary outcomes such as the presence of chronic postsurgical pain measured 6 months after surgery will be compared between study groups using Chi-square tests. The investigator that will be in charge of the statistical analyses will be blinded to group assignment. As a secondary analysis aiming at understanding the underlying changes over time in QST, pain intensity and catecholamine concentrations will be examined using repeated measures analyses.

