4 PRELIMINARY DATA AND CLINICAL DATA

In a previous study, we have demonstrated that presence of pain before surgery was the best predictor of pain intensity after surgery in Adolescent Idiopathic Scoliosis (AIS) patients undergoing surgery [30]. Pain before surgery was reported by 48% of the cohort (n=50) (Figure 1). We also demonstrated that intensity of pain in the first days after surgery was associated with pain intensity weeks after surgery, thus demonstrating the clinical need to improve preoperative and acute pain management in order to minimize long-term consequences.

Figure 1. Patients reporting preoperative pain had greater postoperative pain intensity levels during the first postoperative 24 hours (POD1, $r=0.47$, $p=0.001$) (A), the second 24 hours (POD2, $r=0.35$, $p=0.025$) (B) and at follow-up appointment (4-6 weeks after surgery, $r=0.50$, $p<0.001$) (C). The pain intensity during POD1 was also predictive of the pain intensity during POD2 ($r=0.74$, $p<0.001$) (D) and at follow-up (6 weeks post-surgery, $r=0.43$, $p=0.005$) (E) (Ferland et al. 2016, PMID: 26852092).

In the same cohort, we also quantified neurotransmitters known to be related to pain. The preoperative plasma levels of norepinephrine metabolite metanephrine concentrations revealed to be associated with the postoperative pain intensity (Figure 3). Although preliminary, these results suggested that preoperative inter-individual differences, could explain postoperative pain trajectories.

[figure not shown]
[figure not shown]

[figure not shown]
Figure 2. Preoperative monoaminergic levels on postoperative pain intensity. The preoperative metanephrine plasmatic levels of AIS patients scheduled for surgery. Patients who reported greater pain intensity at 6 weeks after surgery had higher metanephrine plasmatic levels before surgery (n=50, $P<0.001$) (Ferland et al., manuscript in preparation).

In the largest study to examine longitudinal pediatric pain trajectories after spine surgery, Sieberg et al proposed perioperative trajectories of pain experience may be better explained by changes in the central pain modulation rather than in the surgical stimulus itself (Figure 3).

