8.2 RECRUITMENT

Patients will be recruited from outpatient clinics at the Shriners Hospital for Children - Canada. Potential participants will be identified and informed of the study by their attending physician at the time of the examination and that presence of back pain is confirmed. If the subject expresses interest in learning more about the study, the physician and and/or a research assistant will then explain the study and answer any questions the subject or their family may have.

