9 STUDY INFORMATION

9.1 BASELINE VISIT

The expected duration for the patient's participation in the research is 6 months and will consist of a baseline visit, In-hospital visit, 6 week post-op visit and a 6 month post-op visit.

At the baseline visit, the subject will be expected to complete the following:

- ✓ Pain intensity rating (self-reported) (Wong Baker Faces Pain Scale)

- ✓ Medical History Interview (Patient History Collection Form)
- ✓ Approximately 10 mL of blood will be drawn and blood pressure will be taken
- ✓ Quantitative Sensory Testing (QST = MDT/PPT/CPM tests)

The subject will be expected to fill out the following questionnaires:

- ✓ Pain numerical rating scale for children (Baseline - 4 questions)
- ✓ State-Trait Anxiety Inventory (STAI-C)
- ✓ Pain Catastrophizing Scale (PCS-C)
- ✓ Functional Disability Index (FDI)
- ✓ Revised Children Anxiety and Depression Scale (RCADS)
- ✓ Pittsburg Sleep Quality Index (PSQI)
- ✓ Neuropathic Pain Questionnaire (DN4)
- ✓ Tampa Scale for Kinesiophobia (TSK)
- ✓ Scoliosis Research Society (SRS-30)
- ✓ Adolescent Pediatric Pain Tool (APPT)

The visit should take approximately 1 hour

Once the subject's CPM results from the baseline visit have been assessed, the subject will be categorized into one of two arms: 1) Sub-optimal endogenous inhibitory response or 2) Optimal endogenous inhibitory response. The sub-optimal group will then be randomized to either Clonidine or the placebo, and the optimal group will be also randomized to either Clonidine or the placebo.

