16.3 SAMPLE SIZE DETERMINATION AND POWER / ACCRUAL RATE

The sample size was calculated for the primary outcome (average pain intensity over the past 7 days six months after surgery). Assuming that a 2-point change on the 0–10 pain intensity scale constitutes a clinically meaningful difference [74,76], a standard deviation of 2.0 units, a study design with 3 repeated measurements having a compound symmetry covariance matrix, a power of 90%, a two-sided alpha level of 0.05 and a conservative autocorrelation coefficient (rho) of one,

a minimum of 22 patients per comparison group is required. To prevent reduced power because of patient loss to follow-up and to minimize confounding effects, 35 patients per group will be enrolled (35 x 4 groups = 150 patients in total).

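### Section 16.4 does not say how baseline pain enters the pain model, so the randomised clonidine comparison may gain no precision from the predictor the protocol itself ranks first

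*Combined protocol and SAP*

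**What the plan says.** - **Model.** Section 16.4 describes pain "during the longitudinal follow-up (baseline to six months after surgery), linear mixed models for repeated measures". The listed adjusters are "independent variables to obtain adjusted effects: age, functional outcome score and psychological profile (STAI and PCS scores". A later sentence gives examples of confounders that such a model could handle, including "physical and emotional functioning, clinical characteristics such as medication use or scoliosis parameters". Preoperative pain is in neither list. The section does not say whether baseline pain is a response or a covariate, or which contrast is tested.
- **Evidence on the predictor.** Section 4 reports from the team's own earlier cohort that "presence of pain before surgery was the best predictor of pain intensity after surgery", with r = 0.50 against pain at 4-6 weeks. It adds: "Pain before surgery was reported by 48% of the cohort (n=50").
- **Data collected.** Section 9.1 schedules a "Pain numerical rating scale for children (Baseline - 4 questions") and a faces scale at the baseline visit.
- **Sizing.** Section 16.3 sizes the trial on "average pain intensity over the past 7 days six months after surgery", with a 2-point difference, SD 2.0, three repeated measures and rho of one. It gives a minimum of 22 and an enrolment of 35 per group.
- **Comparisons.** Section 16.5 lists sub-optimal versus optimal responders within placebo, which is not randomised, and clonidine versus placebo within sub-optimal responders, which is.

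**The concern.** The plan adjusts for several variables but does not name the one its own data put first, although that variable is already measured. Having baseline in the time span of a repeated-measures model does not settle this. With a separate mean for each group at each visit and complete data, the estimated six-month group difference is the ordinary difference in six-month means, and the baseline row adds no precision. Baseline pain helps the randomised comparison if it is a covariate, or if it is a response whose group means are held equal, as randomisation justifies. Section 16.4 states neither.

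What is at stake is the width of the interval for the drug effect and the discretion left to the analyst. The timing of the other adjusters is also unstated. The functional disability, anxiety (STAI-C) and catastrophizing (PCS-C) scales are scheduled 3 + 4 + 6 = 13 times, of which 2 + 2 + 5 = 9 fall after study drug starts. Adjusting for a score taken after treatment would condition on a possible result of treatment.

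**Working it through.** **Inputs.** Difference 2, SD 2.0, two-sided alpha 0.05, power 90%, and 22 or 35 per group (section 16.3). The documents give no correlation r between baseline and six-month pain. The reported 0.50 is at 4-6 weeks, in a cohort where about half had preoperative pain. Section 8.2 has patients informed of the study "at the time of the examination and that presence of back pain is confirmed", which may narrow the spread of baseline pain and lower r. I assume r = 0.3 to 0.5.

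**1. The plan's figure.** n = 2(1.960 + 1.282)² × 2²/2² = 21.01, rounded up to 22. With three compound-symmetric measures the variance factor is (1 + 2·rho)/3, which is 1 at rho = 1, so n is again 22. The plan's number reproduces and uses no baseline covariate.

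**2. Standard error (SE) of the six-month difference, 35 per group, no other covariates.**

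| Use of baseline pain | Formula | r = 0.3 | r = 0.5 |
|---|---|---|---|
| Response row, free group means | 2·√(2/35) | 0.478 | 0.478 |
| Change from baseline | 2·√(2(1−r))·√(2/35) | 0.566 | 0.478 |
| Covariate | 2·√(1−r²)·√(2/35) | 0.456 | 0.414 |

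A constrained-baseline model gives about the same gain as the covariate. The cut is 1 − √(1−r²) = 4.6% to 13.4%, equivalent to 1/(1−r²) − 1 = 9.9% to 33.3% more patients. At 22 per group the SE goes from 0.603 to 0.575 or 0.522. A simulation of 20,000 trials at 35 per group gave empirical SEs of 0.476 and 0.479 unadjusted, and 0.459 and 0.418 adjusted, for r = 0.3 and 0.5. All means were 2.00.

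**3. Allowing for the covariates already listed.** Treat them as one composite that explains an assumed 10% of outcome variance (correlation √0.10 = 0.316) and correlates an assumed 0.4 with baseline pain.
- Before: 0.478·√0.90 = 0.454.
- After, R² = (0.10 + r² − 2·0.316·r·0.4)/(1 − 0.4²), which is 0.136 at r = 0.3 and 0.266 at r = 0.5.
- SE = 0.478·√(1 − R²) = 0.444 or 0.410, a cut of about 2% to 10%.
- Patient equivalent: 0.90/(1 − R²) − 1, about 4% to 23%.
- Approximate 95% half-width: 1.96 × 0.454 = 0.89 points, falling to 0.87 or 0.80.

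**4. Power for 2 points** (noncentral t, against no covariates). At 35 per group: 98.5% unadjusted, 99.1% or 99.7% adjusted. At 22 per group: 90.0%, then 92.4% or 96.2%.

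**5. Chance imbalance.** A one-SE baseline difference (0.478) moves the unadjusted estimate by r × 0.478 = 0.14 to 0.24. This is already inside the SE: at r = 0.5, 0.239² + 0.414² = 0.478². It is not a second cost.

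**6. Non-randomised comparison.** If the CPM groups differ by 1.0 point at baseline and CPM has no further effect, a change-from-baseline contrast shows (r − 1) × 1.0 = −0.70 to −0.50. That contrast would mislead here.

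**The case against.** The best reply is that baseline pain is probably in the model already. The model starts at baseline and the sizing assumes three measurements, which fits baseline, six weeks and six months; a response is not normally listed as a covariate too. That reading is likely, so one cannot say that baseline pain is left out altogether. It does not remove the point, because as a response with free means or as a change score it brings no gain at the assumed r (step 2). With dropout the baseline row does some work, but that is not the gain at issue.

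Other objections stand and limit the size. The 4.6% to 13.4% range compares with a model that has no covariates, which is not the plan. The correlation is assumed. The planned test already meets its power target. The calculation also concerns the drug effect, which section 6 makes the secondary objective.

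A reader might infer that the plan will adjust for postoperative medication or follow-up scores. The documents do not say so. Medication appears only among examples of what such models permit, and the word confounders leans towards baseline values. This part is a clarification.

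**Conclusion.** The point holds as an efficiency and specification gap. Section 16.4 should state the role of baseline pain, because only a covariate or a constrained-baseline model recovers the precision and neither is stated. The realistic gain in SE is about 2% to 10%, resting on an assumed r of 0.3 to 0.5 at six months, an assumed 10% of variance explained by the listed covariates, and their assumed correlation of 0.4 with baseline pain. The upper limit, against no covariates, is 4.6% to 13.4%.

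Two stronger readings are not supported. The omission does not bias the clonidine versus placebo estimate, since randomisation protects it. Nor does it make 22 per group wrong or leave the trial underpowered for 2 points, given about 98.5% power at 35 per group.

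Sections 16.1 and 16.4 name both six weeks and six months, while section 16.3 sizes on six months alone. The primary time point should be reconciled as a separate matter.

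**What to change.** 1. **Clonidine versus placebo, sub-optimal CPM.** Model 6-week and 6-month pain with group-by-visit terms and baseline pain NRS, interacting with visit, as a covariate. Alternatively, keep baseline as a response with group means constrained equal. Choose one, not both.
2. **Other adjusters.** State that the functional score, STAI-C and PCS-C are baseline-visit values; STAI-C is also taken on the day of surgery. Keep postoperative medication use and follow-up scores out of the primary model.
3. **Sub-optimal versus optimal CPM within placebo.** Keep the result without baseline pain for the predictive question in section 6, and add one with it to show added prediction. Do not rely on a change-from-baseline contrast.

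The cost is a few sentences in the analysis plan, settled before unblinding, and one check that the four-question baseline NRS form contains the 7-day average item. If it does not, use the baseline NRS item that is collected. No new data, visits or patients are needed.

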6 OBJECTIVES

The primary objective of this study is to evaluate if pre-operative QST can identify if patients will have high pain intensity peri-operatively and at 6 months post-operatively. We will evaluate the intensity and chronicity of pain and the function of the descending inhibitory system through a short QST procedure before surgery and six months after surgery. In addition, we will evaluate the patient's physical and emotional functioning, and explore the potential biological underlying mechanisms at the same time points.

The secondary objective of this study is to determine if the peri-operative use of an alpha-2 adrenergic receptor agonist enhances the efficacy of the descending inhibitory system of patients with sub-optimal CPM efficacy before surgery by decreasing pain after surgery. Consequently, this pharmacological intervention may also reduce the incidence of acute and chronic pain after surgery. We will evaluate the pain intensity and the function of the descending inhibitory system through a short QST procedure six weeks after surgery and six months after surgery in patients receiving Clonidine or placebo during the perioperative period. We will also evaluate the patient's physical and emotional functioning, and explore the potential biological underlying mechanisms at the same time points.

We will also evaluate the potential biomechanical alterations in 3D related to pain in children reporting presence of back pain pre and post spine surgery.

Our hypothesis is that patients undergoing spine surgery with poor inhibitory pain response will have less pain in the immediate and long-term period when treated prophylactically with Clonidine in the perioperative period.

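### Section 16.4 carries a baseline-to-six-months model, with function, STAI and PCS as covariates of unstated timing, over to the continuous secondary outcomes; this permits self-adjustment, and the group-by-time test is an unadjusted change score

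*Combined protocol and SAP*

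**What the plan says.** Section 16.4 describes linear mixed models for pain intensity "during the longitudinal follow-up (baseline to six months after surgery", with these covariates: "age, functional outcome score and psychological profile (STAI and PCS scores". One reason it gives for this type of model is "the possibility to adjust for potential confounders (e.g. patients", and its examples include physical and emotional functioning. It then extends the approach: "Continuous secondary outcomes will be compared between study groups using similar models".

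The section does not state the visit at which the covariates are taken, whether baseline stays in the response for the secondary outcomes, or what happens to a covariate that is itself the outcome. It does not list the continuous secondary outcomes. The one secondary endpoint named in 16.2 and 16.4 is binary chronic postsurgical pain ("CPSP will be defined in a dichotomous way (yes/no"); categorical outcomes "will be compared between study groups using Chi-square tests".

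Under both objectives, Section 6 says the trial will evaluate "physical and emotional functioning, and explore the potential biological underlying mechanisms at the same time points". Sections 9.1 and 9.5 collect the FDI, STAI-C and PCS-C at baseline, six weeks and six months. Section 16.3 plans for three repeated measurements with compound symmetry.

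**The concern.** The scales that most plausibly serve as continuous secondary outcomes for physical and emotional functioning are also the scales on the covariate list. If the pain model is reused for them, the same score can stand on both sides of the equation, and nothing in the plan prevents it.

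There is a second problem, which does not depend on the self-covariate. A response that runs from baseline includes a visit at which randomised groups cannot differ because of treatment. A group main effect is then averaged over that visit, and a group-by-time contrast reduces to change from baseline, which is less precise than follow-up adjusted for baseline.

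At stake are the reported size of the effects on function, anxiety and catastrophizing, and the power to detect them. Depending on how the sentence is read, the analyst could report none, two-thirds or all of the same true effect.

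**Working it through.** **The plan's own figure.** Section 16.3 gives sample-size inputs for pain only: difference 2, SD 2.0, two-sided alpha 0.05, power 90%, rho = 1. With rho = 1 the repeated-measures factor (1 + 2·rho)/3 equals 1. So n per group = 2 × (1.960 + 1.282)² × (2.0/2)² = 21.01, rounded up to 22, as the plan states. It gives no figure for the continuous secondary outcomes.

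**Inputs for the check.** From the plan: 35 per group (16.3), compound symmetry (16.3), and three visits: baseline, six weeks and six months (9.1, 9.5). Assumed, because the plan does not give them: an outcome standardised to SD 1, a true effect of 0.6 SD at both follow-up visits, rho of 0.3, 0.5 or 0.7, and complete data. Write d0, d1, d2 for the observed group differences at the three visits. Under randomisation their expected values are 0, 0.6, 0.6.

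**1. Same-visit value of the same scale as covariate.** The outcome is regressed on itself: the slope is 1, the residual is zero and the group coefficient is 0. In simulation the estimate was 0.00. A less visible form is a same-visit related scale that treatment also shifts, such as PCS when STAI is the outcome. With a correlation of 0.5 between the scales and a true effect of 0.5 SD on both, the expected estimate is 0.5 − 0.5 × 0.5 = 0.25. Simulation gave 0.25.

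**2. Baseline kept in the response, group main effect.**
- Without the own-baseline covariate, the estimate is (d0 + d1 + d2)/3, with expected value (0 + 0.6 + 0.6)/3 = 0.40.
- With it, the fitted slope is on average (1 + 2·rho)/3, so the estimate is (d0 + d1 + d2)/3 − d0(1 + 2·rho)/3 = [(d1 − rho·d0) + (d2 − rho·d0)]/3. Its expected value is again 0.40.

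The factor of two-thirds therefore comes from the baseline visit, not from the covariate. The second expression is exactly two-thirds of the baseline-adjusted estimate averaged over follow-up, so its power equals that of the adjusted analysis. Only the reported size is wrong.

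**3. Baseline kept in the response, group-by-time at six months.** The estimate is d2 − d0. A covariate that is constant within a patient cancels from this contrast, so including the own baseline changes nothing.
- Change score: SE = √[2 × 2(1 − rho)/35]
- Follow-up adjusted for own baseline: SE = √[2 × (1 − rho²)/35]
- Power ≈ Φ(0.6/SE − 1.96)

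| rho | SE, change | Power | SE, adjusted | Power |
|---|---|---|---|---|
| 0.3 | 0.283 | 56% | 0.228 | 75% |
| 0.5 | 0.239 | 71% | 0.207 | 83% |
| 0.7 | 0.185 | 90% | 0.171 | 94% |

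Simulation gives about 56/69/89% against 74/80/93%, within three points of the formula, which uses the normal in place of the t distribution. The variance ratio is 2(1 − rho)/(1 − rho²) = 2/(1 + rho), that is 1.54, 1.33 and 1.18. Simulated type I error is about 5%.

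**4. Follow-up values only as response, own baseline as covariate.** The full effect is recovered. In simulation with a true effect of 0.5 SD the estimate was 0.50, and power averaged over both follow-ups was 79/84/93%, against 72/67/62% for the same response without adjustment.

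**The case against.** The strongest reply is that this is an unclear sentence rather than a wrong analysis. Similar does not mean identical: an analyst modelling STAI could drop STAI from the covariates and still comply. Describing the covariates as potential confounders fits pre-treatment values. The primary endpoint is defined at six weeks and six months only, so a follow-up-only response is open. A same-visit self-covariate leaves zero residual and would be noticed. No continuous secondary outcome is listed, Section 6 names no scale and does not mention catastrophizing, and the functional score is not identified as the FDI. All of this stands. It means the harm is permitted, not certain. It does not remove the gap, because 16.4 itself describes the model as running from baseline.

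Three stronger readings are tempting, and the documents do not support them.
- A reader might infer that self-adjustment is what the plan prescribes. It prescribes neither covariate timing nor an identical model.
- A reader might infer that the self-covariate causes the dilution or the loss of power. Steps 2 and 3 show that both arise from keeping baseline as a response.
- A reader might infer that, in the non-randomised comparison of placebo patients with sub-optimal and optimal response (16.5), the forced slope over-corrects by 0.17 SD per 1 SD of baseline difference (0.67 − 0.50 at rho 0.5). The main-effect coefficient in step 2 contains d1 − rho·d0 and d2 − rho·d0, so no such shift appears there, and the group-by-time contrast is the same with or without the covariate.

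The power gap also depends on the assumed effect. At 1 SD, the standardised difference that 16.3 implies for pain (2/2.0), change-score power is 94/98/>99% against 99/>99/>99%, so the gap nearly closes.

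**Conclusion.** The point holds as a gap in specification combined with an avoidable loss of efficiency. The wording permits an outcome to be adjusted for its own same-visit value, which would remove the group effect. With baseline covariates, the stated response window gives either a main effect at two-thirds of its true size or a change-score test. At an assumed 0.6 SD with 35 per group, that test gives up about 18, 11 and 4 percentage points of power at rho 0.3, 0.5 and 0.7 (74 − 56, 80 − 69, 93 − 89).

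The effect size and rho are assumptions, and complete data with compound symmetry is taken throughout. In the randomised comparison the change-score test is unbiased and keeps its type I error, so it is weaker rather than invalid. Binary chronic postsurgical pain, tested by chi-square, is untouched. That FDI, STAI-C and PCS-C are the affected outcomes is inferred from Sections 6, 9.1 and 9.5. Fixing covariates at baseline would not be enough, because the change-score result does not depend on the covariate.

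**What to change.** Replace the sentence on continuous secondary outcomes in 16.4 with wording to this effect: *Each continuous secondary outcome will be analysed with its six-week and six-month values as the response, and with its own baseline value and age as covariates. Functional score, STAI and PCS will enter only as baseline values, and only in models where they are not the outcome.* List the continuous secondary outcomes and name the scale meant by the functional score.

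The cost is a short edit to 16.4. All the values needed are already collected at the scheduled visits, and no further data or patients are required.
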